#### 16.4 Data & Safety Monitoring:

- 16.41 The principal investigator(s) and the study statistician will review the study at least twice a year to identify accrual, adverse event, and any endpoint problems that might be developing. The Mayo Clinic Cancer Center (MCCC) Data Safety Monitoring Board (DSMB) is responsible for reviewing accrual and safety data for this trial at least twice a year, based on reports provided by the MCCC Statistical Office.
- 16.42 Adverse Event Stopping Rules (to be evaluated in each arm independently): The stopping rules specified below are based on the knowledge available at study development. We note that the Adverse Event Stopping Rule may be adjusted in the event of either (1) the study re-opening to accrual or (2) at any time during the conduct of the trial and in consideration of newly acquired information regarding the adverse event profile of the treatment(s) under investigation. The study team may choose to suspend accrual because of unexpected adverse event profiles that have not crossed the specified rule below.

Accrual will be temporarily suspended to this study if at any time we observe events with an attribution of possibly, probably, or definitely related to study treatment that satisfy one of the following:

- if 5 or more patients in the first 13 treated patients experience a grade 4 or higher non-hematologic adverse event
- if after the first 13 patients have been treated, 40% of all patients experience a grade 4 or higher non-hematologic adverse event.

We note that we will review grade 4 and 5 adverse events deemed "unrelated" or "unlikely to be related", to verify their attribution and to monitor the emergence of a previously unrecognized treatment-related adverse event.

16.5 Results Reporting on ClinicalTrials.gov:

At study activation, this study will have been registered within the “ClinicalTrials.gov” website. The Primary and Secondary Endpoints along with other required information for this study will be reported on [REDACTED] For purposes of timing of the Results Reporting, the initial estimated completion date for the Primary Endpoint of this study is 5 years after the study opens to accrual. The definition of “Primary Endpoint Completion Date” (PECD) for this study is at the time all patients registered have achieved a confirmed complete response or have discontinued treatment without achieving a confirmed complete response.

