- 1.2 ***Initial therapy of multiple myeloma:*** The treatment paradigms for multiple myeloma have undergone a significant change in the past decade. A decade ago, patients who were considered eligible for transplant underwent the procedure after a brief duration of therapy with a steroid based regimen with or without doxorubicin. Patients ineligible for transplant went on to receive melphalan and prednisone. With these treatment approaches patients had a median survival of 3-4 years, with nearly 10-20% of patients dying in the first year after diagnosis. During the last decade several new drugs were introduced such as thalidomide and its analogue lenalidomide and the proteasome inhibitor bortezomib and these along with continued use of transplant has led to improved survival in myeloma. In fact, in the recent clinical trials 3-year survival has approached 90% and 1-year mortality has dropped to under 2%. This progress has come through a series of investigations examining the efficacy of the new drugs used in various combinations and sequences. Initial trials in the relapsed setting confirmed significant clinical activity for all these new drugs. This was followed by several clinical trials that examined the combination of novel agents with dexamethasone in the setting of newly diagnosed disease. The studies consistently demonstrated superior response rates, deeper responses, and improved progression-free survival for patients undergoing initial therapy with novel agents. The trials examined the role of the new drugs in the context of transplant eligible and ineligible patients. This has been followed by three drug regimens that either combined the new drugs together or incorporated an alkylator drug to the novel agent-dexamethasone combination. These have included combinations of bortezomib and dexamethasone with thalidomide (VTD), lenalidomide (VRd) or cyclophosphamide (VCD).

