**15.47 Known potential toxicities:**

Very common known potential toxicities,  $\geq$  10%:

Injury, poisoning, and procedural complications: infusion related reaction

Infections and infestations: pneumonia, upper respiratory tract infection, bronchitis, pneumonia

Blood and lymphatic system disorders: neutropenia, thrombocytopenia, anemia, lymphopenia

Vascular disorders: hypertension

Nervous system disorders: headache, peripheral sensory neuropathy

Respiratory, thoracic, and mediastinal disorders: cough, dyspnea

Gastrointestinal disorders: nausea, vomiting, diarrhea

Musculoskeletal and connective tissue disorders: muscle spasms

General disorders and administration site conditions: fatigue, pyrexia, peripheral edema

Common known potential toxicities, 1% - <10%:

Injury, poisoning, and procedural complications: infusion related reaction

Infections and infestations: respiratory tract infection, influenza, lower respiratory tract infection, sepsis, sinusitis, rhinitis, pharyngitis, viral respiratory tract infection, tonsillitis, lung infection, herpes zoster  
Blood and lymphatic disorders: febrile neutropenia,  
Cardiac disorders: atrial fibrillation  
Respiratory, thoracic, and mediastinal disorders: pulmonary edema, hypoxia, laryngeal edema, pneumonitis, bronchospasm  
Gastrointestinal disorders: diarrhea

Uncommon and rare known potential toxicities, <1%:  
Infections and infestations: metapneumovirus infection, tracheitis, acute sinusitis, bronchiolitis, epiglottitis, oropharyngeal candidiasis, tracheobronchitis, upper respiratory tract infection bacterial, bronchitis bacterial, respiratory syncytial virus infections, laryngitis, streptococcal pharyngitis, viral rhinitis  
Blood and Lymphatic Disorders: neutropenic sepsis, neutropenic infection  
Please refer to the Investigator Brochure for a more comprehensive list of treatment-emergent adverse events.

15.48 **Drug procurement:** Daratumumab (Darzalex®) will be provided to research subjects for the duration of their participation in this trial at no charge to them or their insurance providers.

15.49 **Nursing Guidelines:**

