### 16.12 Sample Size

The one-stage binomial design to be used in each arm is fully described below. A maximum of 36 evaluable patients will be accrued to each arm of this phase II study unless undue toxicity is encountered. We anticipate accruing an additional 4 patients in each arm to account for ineligibility, cancellation, major treatment violation, or other reasons for a maximum of 40 patients accrued in each arm, and 80 patients overall.

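### The numeric accrual-suspension triggers in Section 16.42 leave out a related death recorded only under a blood-class term and pool every other related death with Grade 4 events

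*Combined protocol and SAP*

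**What the plan says.** Section 16.42 gives two numeric triggers, applied in each arm separately. Accrual is temporarily suspended "if 5 or more patients in the first 13 treated patients experience a grade 4 or higher non-hematologic adverse event", and also "if after the first 13 patients have been treated, 40% of all patients experience a grade 4 or higher non-hematologic adverse event". Both count only "events with an attribution of possibly, probably, or definitely related to study treatment that satisfy one of the following". There is no limit specific to deaths, and the plan states no operating characteristics for this rule.

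The protocol files several infection-type events under a blood class. Febrile neutropenia is there in Sections 8.3, 10.51 and 15.47, and the rare-toxicity list in Section 15.47 has "Blood and Lymphatic Disorders: neutropenic sepsis, neutropenic infection". Section 10.412 provides for deaths to be reported under a CTCAE term.

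Other safeguards exist:

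- **Discretion (16.42):** "The study team may choose to suspend accrual because of unexpected adverse event profiles that have not crossed the specified rule below". The rule may also be adjusted at any time, and Grade 4 and 5 events called unrelated or unlikely are reviewed for attribution.
- **DSMB (16.41):** accrual and safety data are reviewed at least twice a year.
- **Death reporting (10.412):** within 24 hours for any death up to 30 days after the last dose, and for later deaths that are at least possibly related.
- **Section 13.7:** the study may be suspended for safety concerns.

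**The concern.** These triggers are the only numeric safety boundary in the trial. On the natural reading of non-hematologic, a survivable related Grade 4 event outside the blood class counts toward suspension, while a related death recorded only as febrile neutropenia does not.

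That route to death is foreseeable. Section 15 lists neutropenia as very common (at least 10%) for ixazomib, lenalidomide and daratumumab, and febrile neutropenia as very common for lenalidomide. Section 1.5 reports neutropenia in 81% of patients given daratumumab with lenalidomide and dexamethasone.

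Deaths that do count are merged with Grade 4 events against a threshold of 5/13 = 38%, then 40%. The numeric rule is therefore insensitive to an excess of deaths unless non-fatal qualifying events are also frequent.

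**Working it through.** **Inputs from the documents.** First trigger: 5 of 13. Second trigger: 40% of all patients after 13. Arm size: "for a maximum of 40 patients accrued in each arm, and 80 patients overall" (Section 16.12). Related events only, one arm at a time.

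**Assumptions.** The documents give no related-death rate for this regimen, so 2% to 20% is shown. Patients are independent, and the rule is checked after each patient.

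**Method check.** The plan gives no figures for the safety rule, so the exact binomial method was checked against the efficacy table in Section 16.22, P(X ≥ 13) with X ~ Bin(36, p):

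| p | 0.25 | 0.30 | 0.35 | 0.40 | 0.45 |
|---|---|---|---|---|---|
| Plan | 0.09 | 0.26 | 0.51 | 0.74 | 0.89 |
| Recomputed | 0.092 | 0.263 | 0.507 | 0.738 | 0.893 |

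The table reproduces.

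**First trigger.** P(X ≥ 5) with X ~ Bin(13, p). At p = 0.10:

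- 5 events: 1287 × 0.1⁵ × 0.9⁸ = 0.00554
- 6 events: 1716 × 0.1⁶ × 0.9⁷ = 0.00082
- 7 events: 1716 × 0.1⁷ × 0.9⁶ = 0.00009
- 8 or more: under 0.00001

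The sum is 0.0065, or 0.65%.

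**Whole rule.** Let f(n, k) be the probability of k events in n patients with no suspension so far. Then f(n, k) = f(n−1, k)(1−p) + f(n−1, k−1)p. Mass is moved to suspended when k ≥ 5 for n ≤ 13, or k ≥ 0.4n for n = 14 to 40. The later thresholds are, for example, 6 at 15, 8 at 20, 12 at 30 and 16 at 40.

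With deaths as the only qualifying events and all of them counted:

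| Related-death rate | Expected deaths in 40 | First trigger | Either trigger by 40 |
|---|---|---|---|
| 2% | 0.8 | 0.0004% | 0.0004% |
| 5% | 2.0 | 0.03% | 0.03% |
| 10% | 4.0 | 0.65% | 0.69% |
| 15% | 6.0 | 3.4% | 3.8% |
| 20% | 8.0 | 9.9% | 11.5% |

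**Effect of coding at a 10% death rate.** If a share s of deaths is recorded only under blood terms, the counted rate is 0.10 × (1−s). For s = 25% it is 7.5% and the rule fires with probability 0.19%. For s = 50% it is 5% and the probability is 0.03%.

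**Effect of other events at a 10% death rate.** If a further share g of patients has a non-fatal related Grade 4 non-hematologic event, the counted rate is 0.10 + g:

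| g | Counted rate | Either trigger by 40 |
|---|---|---|
| 0 | 10% | 0.69% |
| 5% | 15% | 3.8% |
| 10% | 20% | 11.5% |
| 20% | 30% | 43.8% |

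**Illustrative separate counts of related deaths, any class.** Binomial tails in 40 patients:

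| Count | At 2% | At 5% | At 10% |
|---|---|---|---|
| at least 2 of 40 | 19.0% | 60.1% | 92.0% |
| at least 3 of 40 | 4.6% | 32.3% | 77.7% |

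**The case against.** Leaving hematologic events out of the rule is defensible. Section 10.41 treats Grade 4 cytopenias as expected, and counting them would trip the rule routinely. This stands for Grade 4 events, but gives no reason to leave out deaths.

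A reader might infer that a related death coded to a blood term can never count. The documents do not support that. Section 16.42 does not define non-hematologic by system organ class, and it counts patients, not terms. Section 10.51 lists sepsis under infections, to be graded at each evaluation, and Section 15.47 lists pneumonia and sepsis there too. A patient with a blood-class death still counts if a related Grade 4 or higher event of that kind is also recorded. The gap concerns deaths recorded only under a blood-class term.

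A reader might also infer that a 10% related-death rate would almost never halt accrual. That goes too far as well. The 0.7% describes the numeric rule alone, with no other qualifying event in any patient. Deaths would be seen case by case through expedited reporting, and the study team could suspend. Still, none of these safeguards sets a number or obliges a suspension. The discretionary clause speaks of unexpected profiles, while Section 10.2 ties expectedness to the Section 15 lists, where febrile neutropenia appears. At 3 evaluable patients a month (Section 16.13), about 3 × 6 = 18 could enter an arm between twice-yearly DSMB reviews, more than the 13-patient window.

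Finally, the one-year mortality of under 2% in Section 1.2 comes from other trials. It is not a related-death rate over up to 36 months of treatment, so it gives context but no benchmark for this regimen.

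**Conclusion.** The point holds for the two numeric triggers. On the natural reading of non-hematologic, a related death recorded only under a blood-class term counts toward neither, and other related deaths carry no more weight than a Grade 4 event. With deaths as the only qualifying events, the chance of a numeric suspension in an arm of 40 is 0.7% at a 10% related-death rate, when about 4 deaths would be expected. It is lower if some deaths are recorded only under blood terms, and higher if non-fatal qualifying events occur as well (11.5% with a further 10% of patients).

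The death rates are assumptions. The result does not show that the protocol as a whole cannot respond to deaths. It shows that the response would rest on judgment and on how the event is coded. This is a cheap improvement worth making to a design choice, and it corrects no error in the plan's figures.

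**What to change.** In both bullets of Section 16.42, widen the qualifying event so that it also takes in a Grade 5 adverse event in any system organ class, and keep the existing attribution filter. This is a short addition to each bullet, and the section already allows the rule to be adjusted during the trial. The downside is a slightly higher chance of a temporary accrual pause. It closes the coding gap but does not change the 0.7%, which already assumes that every death counts.

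Optionally, the sponsor and DSMB may consider a separate count of related deaths that prompts DSMB review across all 40 patients in an arm, with its operating characteristics stated. The threshold is theirs to set, and the trade-off is real. At least 2 of 40 would fire with probability 19% at a 2% rate and 92% at 10%. At least 3 of 40 would fire with 4.6% and 78%.

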16.6 Inclusion of Women and Minorities

16.61 This study will be available to all eligible patients, regardless of race, gender, or ethnic origin.

16.62 There is no information currently available regarding differential effects of this regimen in subsets defined by race, gender, or ethnicity, and there is no reason to expect such differences to exist. Therefore, although the planned analysis will, as always, look for differences in treatment effect based on racial and gender groupings, the sample size is not increased in order to provide additional power for subset analyses.

16.63 The geographical region served by MCCC has a population which includes approximately 3% minorities. Based on prior MCCC studies involving similar disease sites, we expect about 3-5% of patients will be classified as minorities by race and about 33% of patients will be women. Expected sizes of racial by gender subsets are shown in the following table:

**16.631 Accrual Estimates by Gender/Ethnicity/Race**

Ethnic Category	Sex/Gender			
	Females	Males	Unknown	Total
Hispanic or Latino	0	2	0	2
Not Hispanic or Latino	28	50	0	78
Ethnic Category: Total of all subjects*	28	52	0	80
Racial Category				
American Indian or Alaskan Native	0	0	0	0
Asian	0	0	0	0
Black or African American	2	2	0	4
Native Hawaiian or other Pacific Islander	0	0	0	0
White	26	50	0	76
Racial Category: Total of all subjects*	28	52	0	80

**Ethnic Categories:** **Hispanic or Latino** – a person of Cuban, Mexican, Puerto Rico, South or Central American, or other Spanish culture or origin, regardless of race. The term “Spanish origin” can also be used in addition to “Hispanic or Latino.”

**Not Hispanic or Latino**

**Racial Categories:** **American Indian or Alaskan Native** – a person having origins in any of the original peoples of North, Central, or South America, and who maintains tribal affiliations or community attachment.

**Asian** – a person having origins in any of the original peoples of the Far East, Southeast Asia, or the Indian subcontinent including, for example, Cambodia, China, India, Japan, Korea, Malaysia, Pakistan, the Philippine Islands, Thailand, and Vietnam. (Note: Individuals from the Philippine Islands have been recorded as Pacific Islanders in previous data collection strategies.)

**Black or African American** – a person having origins in any of the black racial groups of Africa. Terms such as “Haitian” or “Negro” can be used in addition to “Black or African American.”

**Native Hawaiian or other Pacific Islander** – a person having origins in any of the original peoples of Hawaii, Guam, Samoa, or other Pacific Islands.

**White** – a person having origins in any of the original peoples of Europe, the Middle East, or North Africa.

**17.0 Pathology Considerations/Tissue Biospecimens: None****18.0 Records and Data Collection Procedures**

## 18.1 Submission Timetable

Data submission instructions for this study can be found in the Data Submission Schedule.

## 18.2 Event monitoring

See [Section 4.2](#) and data submission table for the event monitoring schedule.

## 18.3 CRF completion for non-Mayo Clinic sites

This study will use Medidata Rave for remote data capture (rdc) of all study data.

## 18.4 Site responsibilities

Each co-sponsor/participant will be responsible for insuring that all materials contain the patient's initials, MCCC registration number, and MCCC protocol number. Patient's name must be removed.

## 18.5 Supporting documentation

This study requires supporting documentation for diagnosis and progression prior to study entry as well as for evidence of response to study therapy and progression after study therapy. Supporting documentation for diagnosis will include either a pathology report or a laboratory report demonstrating multiple myeloma with extramedullary disease or plasma cell leukemia (including bone marrow biopsy report; and SPEP, UPEP, FLC, FISH, and Cytogenetics reports). These reports should be submitted within 14 days of registration.

For progression of disease prior to study entry, supporting documentation includes the evidence needed to determine the patient's progression prior to enrollment. These documents should be submitted within 14 days of registration.

For response to treatment, supporting documentation includes SPEP, UPEP, FLC, Serum and Urine Immunofixation, Bone Marrow Biopsy and aspirate, and X-ray skeletal survey. For patients who progress after study therapy supporting documentation may include any of the following: SPEP, UPEP, FLC, serum and urine immunofixation, bone marrow biopsy and aspirate, and X-ray skeletal survey.

## 18.6 Labelling of materials

Each participant will be responsible for insuring that all materials contain the patient's initials, MCCC registration number, and MCCC protocol number. Patient's name must be removed.

## 18.7 Incomplete materials

Any materials deemed incomplete by the MCCC Operations Office will be considered "not received" and will not be edited or otherwise processed until the missing information is received. A list of the missing documents will be made available to the appropriate co-sponsor/participant.

## 18.8 Overdue lists

A list of overdue materials and forms for study patients will be generated monthly. The listings will be sorted by location and will include the patient study registration number. The appropriate co-sponsor/participant will be responsible to obtain the overdue material.

18.9 Corrections forms

If a correction is necessary the QAS will query the co-sponsor/participant. The query will be sent to the appropriate co-sponsor/participant who will make the correction and return the query and documentation of correction back to the QAS.

**19.0 Budget**

- 19.1 Costs charged to patient: Routine clinical care
- 19.2 Tests to be research funded: None
- 19.3 Other budget concerns: None

## Appendix I    Multiple Myeloma Diagnostic Criteria

### **Clonal BMPC $\geq 10\%$ or biopsy-proven plasmacytoma PLUS**

#### **-Either a myeloma defining event:**

**C:** Hypercalcemia: serum calcium  $>1$  mg/dL higher than the upper limit of normal or  $>11$  mg/dL

**R:** Renal insufficiency: creatinine clearance  $<40$  mL per min or serum creatinine  $>2$  mg/dL

**A:** Anemia: hemoglobin  $>20$  g/L below the lower limit of normal, or a hemoglobin  $<100$  g/L

**B:** Bone lesions: osteolytic lesions on x-ray, CT, or PET-CT

#### **-OR a biomarker of early progression**

- Clonal bone marrow plasma cell percentage  $\geq 60\%$
- Involved: uninvolved serum free light chain ratio  $\geq 100$
- $>1$  focal lesion on MRI studies

**Appendix II Mayo Risk Stratification (mSMART)****High Risk**

FISH deletion 17p

FISH t(4:14)

FISH t(14:16)

Hypodiploidy

PCLI >3%

**Standard Risk**

Not high risk as defined above

**Appendix III NYHA Classification**

Class I: NO Symptoms with ordinary activity

Class II: Symptoms with ordinary activity

Class III: Symptoms with minimal activity

Class IV: Symptoms at rest

**Appendix IV ECOG Performance Status Scale**

SCORE	DESCRIPTION
0	Fully active, able to carry on all pre-disease performance without restriction.
1	Restricted in physically strenuous activity but ambulatory and able to carry out work of a light or sedentary nature, e.g., light housework, office work.
2	Ambulatory and capable of all self-care but unable to carry out any work activities. Up and about more than 50% of waking hours.
3	Capable of only limited self-care, confined to bed or chair more than 50% of waking hours.
4	Completely disabled. Cannot carry on any self-care. Totally confined to bed or chair.
5	Dead.

## Appendix V Revlimid REMS Required Pregnancy Information

### Risks of Fetal Exposure, Pregnancy Testing Guidelines and Acceptable Birth Control Methods Risks Associated with Pregnancy

The use of lenalidomide in pregnant females and nursing mothers has not been studied nor has the effect of the lenalidomide on human eggs and sperm. The risks to a fetus are not known. However, because lenalidomide is related to thalidomide, and thalidomide is known to cause severe birth defects, the following requirements must be observed.

Females of childbearing potential (FCBP)† must agree to use two reliable forms of contraception simultaneously or to practice complete abstinence from heterosexual intercourse during the following time periods related to this study: 1) for at least 28 days before starting study drug; 2) while participating in the study; and 3) for at least 28 days after discontinuation from the study. The two methods of reliable contraception must include one highly effective method (i.e. intrauterine device (IUD), hormonal [birth control pills, injections, or implants], tubal ligation, partner's vasectomy) and one additional effective (barrier) method (i.e. latex condom, diaphragm, cervical cap). FCBP must be referred to a qualified provider of contraceptive methods if needed.

